10.4.2 Justification for Dose

The planned starting and target doses of AZD4573 for Module 1 are as per the RP2D already determined for lymphoma in the ongoing Phase I monotherapy study of AZD4573 (D8230C00001).

CCI
CCI

These Grade 4 AST elevations met the definition of DLT in versions 2 and 5 of the protocol (dated 7 July 2017 and 18 April 2019), but were transient (less than 4 days duration) and were not accompanied by clinical signs and symptoms of significant hepatic dysfunction. Review of the data (December 2019) by AstraZeneca's Hepatic Safety Knowledge Group and external industry and academic experts concluded that isolated asymptomatic reversible Grade 4 enzyme elevations should not be regarded as DLTs unless prolonged and accompanied by other clinical changes. Study investigators concurred with this interpretation and the protocol was amended accordingly to update the DLT definition. The protocol version including the revised DLT definition has been approved by competent authorities in the United Kingdom, Netherlands, and Germany.

CCI
CCI
CCI
CCI
CCI
CCI

Furthermore, exploratory data from CCI samples collected from ongoing Phase I monotherapy study support target engagement CCI at all doses tested to date (ie, 6 mg and above), with a median CCI of CCI (range: CCI CCI) observed following the 12 mg weekly regimen (based on preliminary PK/PD modelling). Corresponding biological effects, eg, CCI CCI have also been observed.

In addition, based on exposure versus safety analysis conducted for the Phase I monotherapy

study, CCI
CCI
CCI

Overall, these analyses support the evaluation of AZD4573 12 mg, once weekly, monotherapy regimen in the treatment of patients with r/r PTCL or r/r cHL.

The clinical data will be used to refine a PK/pharmacodynamics/efficacy model, and future decisions on dose regimens and escalations will be based on the observed clinical data to date and this refined model.

10.4.3 End of Module Definition

Refer to Section [4.4](#) in the core protocol for the end of study definition.

The end of module is defined as the last scheduled visit or contact of the last participant enrolled in the module.

All participants will continue to be followed for survival after objective disease progression until death, lost to follow-up, AstraZeneca closes the Module, or withdrawal of consent, whichever occurs first, up to the final analysis DCO.

Any participants still receiving study intervention at the completion of the final analysis will be able to continue to receive the intervention at the sponsor's discretion for up to 2 years, if the participant is still considered to be deriving clinical benefit and the sponsor is continuing development of the IP. Such participants will continue to be monitored for all SAEs up to 30 days after the last dose of the intervention therapy. Participants who continue to demonstrate clinical benefit after this 2 year treatment period will be eligible to receive AZD4573 as monotherapy or as part of a combination therapy via a rollover study requiring approval by the responsible Health Authority and ethics committee or through another mechanism at the discretion of the sponsor.

10.4.4 Safety Review Committee

A study-specific SRC will provide ongoing safety surveillance of the study, with regularly scheduled reviews of safety, PK, and other relevant data.

The SRC will be responsible for making recommendations for dose confirmation or modification. All participants will be followed for safety through the entire duration of treatment.

A comprehensive initial review of all safety data will be conducted in approximately the first 6 participants of each cohort (safety run-in), with separate SRCs for each cohort executed independently. Recruitment will not be paused during this review. These participants will be

followed until all have completed Cycle 1, to ensure the treatment schedule is safe and tolerable. The SRC will review the totality of all relevant data (eg clinical, laboratory, safety) prior to providing decisions on study conduct. All decisions by this committee will be documented and shared in writing with all participating sites.

If, on an ongoing basis, > 25% of participants experience any AEs related to study intervention that result in discontinuation of study treatment, study data will be evaluated by the SRC. Enrolment may be paused until the safety data review by the SRC has been completed. Following this SRC review, additional monitoring may be implemented and/or enrolment and dosing may resume at a lower dose level or on a modified schedule. The SRC will meet at least every 6 months to review the overall safety and clinical data from the study.

At any time point during the study, the occurrence of a fatal AE deemed related to study therapy (after full etiological work-up and in discussion with the SRC) will result in study drug interruption and a comprehensive review of safety.

10.5 Study Population – Module 1

Refer to Section 5.1 and Section 5.2 in core protocol for inclusion and exclusion criteria, respectively.

10.6 Study Intervention – Module 1

AZD4573 is administered as an absolute (flat) dose, 2-hour (\pm 15 minutes) intravenous infusion on a once weekly schedule. CCI

Arm name	N/A
Intervention name	AZD4573
Type	Drug
Dose formulation	Concentrate for solution for infusion
Unit dose strength(s)	1.5 mg/ml
Dosage level(s)	6 mg AZD4573 (starting dose) 9 mg AZD4573 12 mg AZD4573 (target dose)
Route of administration	IV infusion
Use	Experimental
IP or NIP	IP
Sourcing	Provided centrally by the sponsor
Packaging and labelling	Study Intervention will be provided in a clear glass vial. Each vial will be labelled as required per country requirement.
Former names	AZ13810325

IP, investigational product; IV, intravenous; NIP, non-investigational product.

10.6.1 Dose Modification

Dose modification and discontinuation guidelines for haematological and non-haematological toxicities (excluding abnormal liver chemistry test results) are shown below in [Table 11](#). Dose modifications for AZD4573 for abnormal liver chemistry test results are described in [Table 12](#).

In general, if a participant experiences a Grade 1 or Grade 2 haematological or non-haematological toxicity, no dose modification is required. If a participant experiences a Grade 3 or Grade 4 toxicity, not attributable to the disease or disease-related processes under investigation, dosing will be interrupted and/or the dose reduced (see [Table 11](#) for recommended dose modifications for AZD4573) and supportive therapy administered as required. If the toxicity resolves or reverts in line with the dose modification guidelines below and the participant was showing clinical benefit, treatment with study treatment(s) may be restarted.

If the toxicity does not resolve in line with the dose modification guidelines below, then the participant should be discontinued from the study treatment and observed until resolution of the toxicity. Maximal drug interruption allowed for AZD4573 is 21 consecutive days; in cases where more than 21 days are needed, a decision to continue, modify, or discontinue study treatment will be made on a case-by-case basis in consultation with the principal investigator and the Study Physician.

Table 11 Recommended Dose Modifications for AZD4573

Event ^a	Occurrence	Action with AZD4573	
Tumour Lysis Syndrome (TLS)			
Changes in uric acid, potassium, phosphorus, creatinine or calcium, or symptoms suggestive of TLS	Any	For any abnormal changes present before dosing, initiate supportive therapy and hold drug for up to 7 days. If not resolved, reduce by 1 dose level.	
		For events of Howard Grade 1 or 2 TLS, resume at same dose level upon resolution.	
		For first occurrence of Howard Grade 3 TLS resume at the same dose upon resolution to Grade 1.	
		For second occurrence of Howard Grade 3 TLS, after resolution to Grade 1, reduce dose by 1 dose level when re-starting AZD4573 except events that in the opinion of the investigator, in consultation with the Study Physician, are not dose limiting.	
		For subsequent occurrences of Howard Grade 3 TLS, further re-challenge and dose level to be discussed with the Study Physician.	
For events of Howard Grade 4 TLS, discontinue AZD4573.			
Non-haematological toxicities (except liver dysfunction and TLS)			

Event ^a	Occurrence	Action with AZD4573
Grade 3 or 4 non-haematological toxicities	First occurrence	
Withhold dosing with AZD4573 until the toxicity has resolved to Grade 1, but no longer than 21 days^b.
 
Adequate supportive therapy as per Institutional guidelines should be given.
 
After resolution of Grade 3 event to Grade 1, AZD4573 therapy may be resumed at the same dose. No dose modification is required.
 
After resolution of Grade 4 event to Grade 1, reduce dose by one dose level when re-starting AZD4573.

	Second occurrence	
Withhold dosing AZD4573 up to 21 days^b.
 
Adequate supportive therapy as per Institutional guidelines should be given.
 
After resolution to Grade 1, reduce dose by one dose level when re-starting AZD4573.
 
If no resolution within 21 days discontinue AZD4573^b.

	Third occurrence	Discontinue AZD4573.
Haematological Toxicities		
Grade 3 or 4 neutropenia without fever or infection, lasting > 7 days despite growth factor support	First occurrence	
Withhold dosing AZD4573 until Grade \leq 2 or baseline level.
 
Restart at same dose level following resolution.

	Second and subsequent occurrences	
Withhold dosing AZD4573 until Grade \leq 2 or baseline level.
 
Restart with 1 dose level reduction following resolution.
 
In case of subsequent occurrences, dosing may be modified to skip weekly dose(s) (eg, 2 weeks on/1 week off or to 1 week on/1 to 2 weeks off), after discussing with the Study Physician.

Grade 3 or 4 neutropenia with infection or fever	First occurrence	
Withhold dosing AZD4573.
 
To reduce the infection risks associated with neutropenia, G-CSF may be administered with AZD4573 if clinically indicated/required as per Institutional practice.
 
Consider secondary prophylaxis with G-CSF as per ASCO/ESMO guidelines. Once the toxicity has resolved to \leq Grade 2 or to baseline level, AZD4573 therapy may be resumed at the same dose.

	Second occurrence	
Withhold dosing AZD4573.
 
Consider using G-CSF as clinically indicated/as per Institutional practice. Follow dose reduction guidelines when resuming treatment with AZD4573 after resolution.
 
Reduce dose by 1 dose level.

Event ^a	Occurrence	Action with AZD4573
	Third occurrence	Discontinue AZD4573.
Grade 3 thrombocytopenia without bleeding	Any	Withhold AZD4573 until Grade \leq 2 or baseline level. Restart AZD4573 at the same dose level.
Grade 4 thrombocytopenia without bleeding requiring blood or platelet transfusion	First occurrence	Withhold AZD4573 until Grade \leq 2 or baseline level. Restart AZD4573 at the same dose level.
	Second occurrence	Withhold AZD4573 until Grade \leq 2 or baseline level. Restart AZD4573 with 1 level dose reduction. If not recovered to Grade \leq 2 or baseline level discontinue.
	Third occurrence	Discontinue AZD4573.
Grade 3 or 4 thrombocytopenia with bleeding requiring blood or platelet transfusion	First occurrence	Withhold AZD4573 until Grade \leq 2 or baseline level. Restart AZD4573 with 1 level dose reduction. If not recovered to Grade \leq 2 or baseline level discontinue.
	Second occurrence	Discontinue AZD4573.

^a Adverse reactions are graded using NCI CTCAE version 5.0.

^b In cases where more than 21 days are needed, a decision to continue, modify, or discontinue study treatment will be made on a case-by-case basis in consultation with the principal investigator and the Study Physician.

Abbreviations: ANC, absolute neutrophil count; ASCO, American Society of Clinical Oncology; ESMO, European Society for Medical Oncology; G-CSF, granulocyte-colony stimulating factor.

Dose modifications for AZD4573 for abnormal liver chemistry test results are described in [Table 12](#).

Table 12 Recommended Dose Modifications for AZD4573 for Abnormal Liver Chemistry Test Results

Event ^a	Action
Isolated^b elevations in ALT, AST, or bilirubin	
Grade 1 Isolated ALT/AST \leq 3 \times ULN or Isolated Bilirubin \leq 1.5 \times ULN	Maintain current dose level. Monitor ALT, AST, ALP, and bilirubin at least 1x per week.

Event ^a	Action
Grade 2 Isolated ALT/AST > 3 to $\leq 5 \times$ ULN or Isolated Bilirubin > 1.5 to $\leq 3 \times$ ULN	After 7 days if hepatic enzymes resolve to Grade ≤ 1 , re-challenge at same dose level.
Grade 3 Isolated ALT/AST > 5 to $20 \times$ ULN	If recovered to Grade ≤ 1 within 7 days, allow re-challenge at same dose level. If not recovered to baseline level within 7 days, discontinue AZD4573.
Grade 3 Isolated Bilirubin > 3 to $10 \times$ ULN	If recovered to baseline level within 96 hours (-2/+12 hours) of start of dose allow re-challenge at same dose level. If not, discontinue AZD4573.
Grade 4 Isolated ALT > $20 \times$ ULN or Isolated Bilirubin > $10 \times$ ULN	Discontinue AZD4573.
Grade 4 Isolated elevation ($\geq 20 \times$ ULN) in AST without concomitant elevation in ALT $\geq 20 \times$ ULN or concomitant elevation in TBL $\geq 2 \times$ ULN that fails to return to baseline level within 7 days from start of dosing	Discontinue AZD4573.
Grade 4^c Isolated AST elevation $\geq 20 \times$ ULN without concomitant elevation in ALT $\geq 20 \times$ ULN or TBL $\geq 2 \times$ ULN	First occurrence If recovered to Grade ≤ 1 or baseline level within 7 days of start of dose allow re-challenge at same dose level.
	Second occurrence If recovered to Grade ≤ 1 or baseline level within 7 days of start of dose allow re-challenge with 1 dose level reduction.
	Third occurrence Discontinue AZD4573.
Concurrent elevations in ALT, AST, or bilirubin (Please also refer to the HL appendix in the CSP for actions to be taken in the event of PHL)	
ALT or AST $\geq 3 \times$ ULN with TBL $\geq 2 \times$ ULN (PHL) AND INR $\geq 1.5 \times$ ULN (or $\geq 1.5 \times$ baseline if elevated at baseline) of any duration	Discontinue AZD4573.

Event ^a	Action
ALT or AST $\geq 3 \times$ ULN with the appearance of fatigue, nausea, vomiting, right upper quadrant pain or tenderness, fever, rash, and/or eosinophilia $> 5\%$	Discontinue AZD4573.
ALT or AST $\geq 3 \times$ ULN and TBL $\geq 2 \times$ ULN where TBL does not return to baseline level within 96 hours (-2/+12 hours) from start of dose and/or AST or ALT do not return to baseline level within 7 days from start of dose	Discontinue AZD4573.
Grade 3 elevation ($\geq 5 \times$ ULN) in ALT or AST with TBL elevation above baseline level or ULN, but $< 2 \times$ ULN that do not return to baseline level within 7 days	Discontinue AZD4573.
ALT and AST $\geq 3 \times$ ULN with concomitant TBL $\geq 2 \times$ ULN, NO increase in INR $\geq 1.5 \times$ ULN (or 1.5 \times baseline), and NO fatigue, nausea, vomiting, right upper quadrant pain or tenderness, fever, rash, and/or eosinophilia $> 5\%$	If recovered to Grade ≤ 1 or baseline level within 96 (-2/+12) hours, re-challenge at same dose level ^c .

^a Adverse reactions are graded using NCI CTCAE version 5.0.

^b Elevations in ALT or AST are considered isolated if bilirubin remains below Grade 1, and elevations in bilirubin are considered isolated if ALT and AST remain below Grade 1.

^c Participants who are considered for re-challenge in the event of Grade 4 transaminase increases or PHL must discuss possible risk of hepatotoxicity with the treating physician, who will document this discussion and participant agreement for continued treatment in the medical records.

Adequate supportive therapy as per Institutional guidelines should be given for all toxicities.

Abbreviations: ALP, alkaline phosphatase; ALT, alanine aminotransferase; AST, aspartate aminotransferase; CTCAE, Common Terminology Criteria for Adverse Events; HL, Hy's Law; INR, international normalised ratio; PHL, Potential Hy's Law; TBL, total bilirubin; ULN, upper limit of normal.

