10.6.2.1.2 TLS Monitoring and Management

Please refer to [Appendix G](#) for the definition of TLS and the TLS grading criteria to be used in this study.

All participants will receive TLS prophylaxis during the intra-participant dose ramp-up and be monitored for TLS during the first 24 hours post start of infusion during the intra-participant dose ramp-up (see Sections [10.6.2.1.1](#) and [10.6.2.1.2](#)). If there are no signs of TLS at the 6 hour TLS monitoring assessment, the participant can be managed as an outpatient at the discretion of the investigator and return to the clinic the next day to complete the 24 hour TLS monitoring assessment. Participants showing signs of TLS at 6 hours after the start of infusion must remain admitted for inpatient TLS monitoring approximately every 6 hours (or more frequently if clinically indicated) until the 24 hour TLS monitoring assessment.

Where hospitalisation for longer than the mandated 24 hours is required it should be noted that if this is due to occurrence of an AE then the event must be reported as an SAE, per definition. However, if it is purely for the purposes of extended observation then this does not qualify as an SAE and does not need to be reported.

For all participants, results of safety laboratory testing (haematology and clinical chemistry at a minimum) must be available within 72 hours prior to dosing and must be reviewed by the investigator prior to each administration of AZD4573. For each TLS monitoring timepoint, a TLS Monitoring page in the eCRF is to be filled out.

In particular, the uric acid level must be < ULN prior to the start of each AZD4573 infusion.

It is strongly recommended that for all participants with elevated uric acid (hyperuricaemia) and intermediate/high risk of TLS, prophylaxis should be administered prior to AZD4573 per Section 10.6.2.1.1 and repeated as clinically indicated thereafter as per local standard.

Monitoring for TLS includes checking potassium, calcium, phosphate, uric acid, and creatinine. Fluid balance must be monitored according to institutional standards.

Any participant developing laboratory TLS must be treated promptly for electrolyte abnormalities (such as hyperkalaemia) to prevent arrhythmias/seizures and for elevated uric acid (hyperuricaemia) with rasburicase (0.20 mg/kg/d IV over 30 minutes for up to 5 days) to prevent acute renal failure and monitored closely for signs of progression to clinical TLS.

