10.6.3 Criteria for Restarting Treatment

The criteria to be met before a participant receives further study drug infusions following a pause in treatment, either within 1 cycle or between cycles, is as below:

All participants:

- 1 Participant has recovered from all treatment-related non-haematological toxicity to CTCAE Grade ≤ 2 .
- 2 Recovery of neutrophils $> 1000/\mu\text{L}$ and platelets $> 75000/\mu\text{L}$ or $> 50000/\mu\text{L}$ with bone marrow involvement.
- 3 Participant has recovered from all hepatic toxicity events within the timeframes described in Table 12 above. If biochemical changes in transaminase(s) and total bilirubin are consistent with the definition of HL, the participant may continue to receive study drug only if all abnormalities have resolved within the timeframes specified in Table 5 above, there are no symptoms of liver injury and INR has not increased above $1.5 \times \text{ULN}$ (or $1.5 \times \text{baseline}$). In these circumstances the participant must be made aware of the unknown potential for liver damage with continued exposure to AZD4573 prior to retreatment. Documentation of continued consent is required.

- 4 Recovery of uric acid to < ULN.
- 5 Recovery of changes in uric acid, potassium, phosphorus, creatinine or calcium, or symptoms suggestive of TLS as defined in [Table 11](#).

10.7 Discontinuation of Study Intervention and Participant Discontinuation/Withdrawal – Module 1

See the SoA (Section [10.1.2](#)) for data to be collected at the time of intervention discontinuation and follow-up and any further evaluations that need to be completed.

Please refer to Section [7](#) (Core protocol) for information on discontinuation of study intervention and participant discontinuation/withdrawal.

10.8 Study Assessments and Procedures – Module 1

- Study procedures and their timing are summarised or linked to in the SoA. Protocol waivers or exemptions are not allowed.
- Immediate safety concerns should be discussed with the sponsor immediately upon occurrence or awareness to determine if the participant should continue or discontinue study intervention.
- Adherence to the study design requirements, including those specified in the SoA, is essential and required for study conduct.

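### Table 11 ties a one-level dose reduction to pre-dose TLS changes that have not resolved. For uric acid this contradicts other protocol sections, and at 6 mg no lower level is listed

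*Protocol*

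**What the plan says.** The TLS row of Table 11 (Protocol 10.6.1) covers changes in uric acid, potassium, phosphorus, creatinine or calcium, and symptoms suggestive of TLS. Its occurrence column reads Any. The first instruction begins "For any abnormal changes present before dosing" and continues: "initiate supportive therapy and hold drug for up to 7 days. If not resolved, reduce by 1 dose level".

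Other parts of the protocol address the same situation:

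- Section 10.6.2.1.2: "the uric acid level must be < ULN prior to the start of each AZD4573 infusion". Table 13 footnote d sets the same condition.
- Section 10.6.3 introduces its list as "The criteria to be met before a participant receives further study drug infusions following a pause in treatment". Item 4 requires uric acid to be back below ULN. Item 5 requires "Recovery of changes in uric acid, potassium, phosphorus, creatinine or calcium, or symptoms suggestive of TLS", and its closing words refer the reader to Table 11 for the definition.
- The general text above Table 11: "If the toxicity does not resolve in line with the dose modification guidelines below, then the participant should be discontinued from the study treatment".
- Schedule of Activities footnote c and Section 10.8.2.5: inclusion criteria 10 (uric acid), 13 and 14 (which includes creatinine clearance) must be met to start Cycle 1 and each later cycle.
- The intervention table in Section 10.6 lists three dosage levels: 6 mg (starting), 9 mg and 12 mg (target).

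**The concern.** In the Table 11 row, the dose is reduced because the abnormality has not resolved. A reduced dose takes effect only when it is given, so the literal reading is an infusion at a lower level while the abnormality persists. Other sections do not allow that for uric acid, and the general text points to a third outcome, discontinuation.

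The protocol classes TLS as an important identified risk. It plans about 30 centres in 10 countries, so different sites could reach different actions for the same patient. The analysis would be affected too. The SAP tabulates AEs leading to dose reduction, delay, interruption and discontinuation separately (5.6.2.2), so the same finding, where reported as an AE, could be counted under different headings depending on which section a site followed.

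**Working it through.** No arithmetic bears on the main point, so the texts are compared directly.

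**Step 1. Is the row worded differently from its neighbours?** Tables 11 and 12 contain eight other fixed one-level reductions:

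- second Howard Grade 3 TLS
- first Grade 4 non-haematological toxicity
- second Grade 3 or 4 non-haematological toxicity
- second and later prolonged neutropenia without fever or infection
- second neutropenia with infection or fever
- second Grade 4 thrombocytopenia without bleeding
- first Grade 3 or 4 thrombocytopenia with bleeding
- second isolated Grade 4 AST elevation

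All eight apply after recovery. The Howard Grade 3 entry in the same TLS block is an example: "after resolution to Grade 1, reduce dose by 1 dose level when re-starting AZD4573". Only the row at issue ties the reduction to non-resolution.

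**Step 2. What happens to a participant on treatment whose change persists after the 7-day hold?**

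| Change | Table 11 row, read literally | Other sections | Result |
|---|---|---|---|
| Uric acid | Reduce one level | Below ULN before an infusion (10.6.2.1.2; Table 13 footnote d; 10.6.3 item 4); also at each cycle start (criterion 10) | Contradiction |
| Creatinine | Reduce one level | Recovery as defined in Table 11 (10.6.3 item 5); creatinine clearance at least 60 mL/min at each cycle start (criterion 14) | Circular reference, with a partial check at cycle start |
| Potassium, phosphorus, calcium, symptoms | Reduce one level | Recovery as defined in Table 11 (10.6.3 item 5) | Circular reference |

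The reference is circular because this row gives no threshold for recovery.

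The general rule in 10.6.1 sits uneasily with the row but does not flatly contradict it. It applies when a toxicity fails to resolve in line with the guidelines in the tables, and this row's own guideline for that case is a reduction.

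**Step 3. Can the reduction be carried out at every level?** The listed levels are 6, 9 and 12 mg.

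- From 12 mg, one level down is 9 mg.
- From 9 mg, one level down is 6 mg.
- From 6 mg, nothing lower is listed.

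Week 1 of Cycle 1 is given at 6 mg, and the row applies to any occurrence.

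**Step 4. How much of this arises before the first infusion?** Criteria 10 and 14 must be met to start Cycle 1, so raised uric acid or low creatinine clearance already prevents the start. Section 10.6.3 concerns a pause in treatment and does not govern a first dose. What remains is mainly potassium, phosphorus, calcium or symptoms. The 6 mg question also arises for anyone already reduced to that level.

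**The case against.** The strongest reply is that the row sets a dose level and Section 10.6.3 sets the condition for restarting, so the two can be read together: hold, wait for recovery, then restart one level lower. The general text also makes restarting depend on resolution and allows an interruption of up to 21 days, with a case-by-case decision beyond that. This reading is possible. The row does not state it, though, and the eight other reductions do state their recovery condition, so a site cannot be expected to supply it.

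The second reply concerns scope, and it stands. A reader might infer that the protocol forbids infusion outright until every TLS analyte has recovered, and that Table 11 overrides this for all of them. The documents do not support that. The unconditional pre-infusion limit is for uric acid only; for the others, Section 10.6.3 item 5 points back to Table 11.

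The third reply also stands. A reader might infer that the row leaves nothing to do at the first infusion. In fact the hold and supportive therapy remain possible, and criteria 10 and 14 screen out part of the problem beforehand. The missing level below 6 mg is also a general gap, since it affects every one-level reduction for a participant at 6 mg. It is not evidence of the uric acid conflict. There is a redaction just above the intervention table, but the dosage-level entry itself is legible.

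Finally, there are safeguards: mandatory TLS prophylaxis, exclusion of PTCL participants with bulky disease or LDH above 3 × ULN, and continued hospital stay for TLS or suspected TLS until it resolves. These make a harmful misreading less likely but do not remove the inconsistency.

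**Conclusion.** The row is wrong as written, as an internal contradiction of limited extent. On its literal reading it conflicts with three explicit statements about uric acid before infusion. For potassium, phosphorus, calcium and creatinine the defect is a circular cross-reference with no recovery threshold. Separately, the reduction step has no listed level to go to at 6 mg.

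The uric acid conclusion assumes that the reduction is meant to be followed by dosing without a further recovery condition, which is what the row says when read alone. If the intended meaning was a reduction at a later restart after recovery, the defect is an omitted condition, and the row still needs correcting. The number of participants affected is unknown, because the documents give no frequency for pre-dose changes that outlast the hold.

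**What to change.** The sponsor should reconcile the Table 11 TLS row, the general text of 10.6.1, Section 10.6.2.1.2, Table 13 footnote d, Section 10.6.3 items 4 and 5, and the cycle-start criteria in Schedule of Activities footnote c and Section 10.8.2.5. After that:

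- one outcome should apply to pre-dose changes that remain unresolved after the hold;
- recovery should be defined in one place for each analyte, so that item 5 refers to an actual criterion;
- the row should say what it means for a participant at the lowest level listed in Section 10.6.

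Which rule or dose should apply is a clinical decision for the sponsor, and none is proposed here. The cost is rewording one table row and its cross-references in a protocol amendment. Sample size and the planned analyses do not change.
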